We will pilot Screening Wizard in two community pediatric practices using a stepped wedge design (n=2 clinics, 50 adolescents).

Hypothesis 1b: Screening Wizard will increase the rate of personalized referrals, compared to TAU. We will perform multilevel modeling to explore time effects and intervention-level factors associated with Screening Wizard. We will first conduct t-tests for continuous variables and chi-square tests for categorical variables to examine for baseline differences in demographic and clinical variables. We will use generalized linear mixed models (nesting for site) to examine for between-intervention differences in personalized referral rate. Baseline characteristics distinguishing groups will be included as covariates in models examining treatment effects. Criterion for success: 75% of PCP recommendations partially or completely match Screening Wizard personalized referral and there is a 50% increase in number of parents and adolescents who feel their needs were met after the PCP visit during the Screening Wizard phase compared to TAU.

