
Screening Wizard will be developed with iterative feedback from end-users (both families and PCPs) using principles of user-centered design with the assistance of the ETUDES Methods Core in conducting qualitative studies described below. A decision tree based on available evidence and expert consensus will determine personalized treatment recommendations with input from the measures as described above. The flowchart for the decision tree will be refined during the usability (phase 1a) and feasibility (phase 1b) phases of the study and will include an immediate referral to a suicidality intervention provided by the primary care clinic staff if high suicidality is identified by PHQ-9 item 9 and the adaptive suicide assessment. The decision tree will prioritize decisions as to how quickly patients should be seen, and in what sector based on suicidality, depression severity, parent perception of adolescent functioning, and presence of

comorbidities. The default treatment recommendations made based on depression severity will then be modified based on: 1) readiness for treatment and 2) treatment preference considering A) congruence between the adolescent and parent, B) depression knowledge, and C) identified barriers. We will also inquire about family history of bipolar illness. The NuReIm team and Methods Core will support integration with the Epic EHR at this stage.

In the Phase 1b, Feasibility, we will test the feasibility of using Screening Wizard in two community pediatric practices (n=50) using a stepped wedge design. We hypothesize that participants, parents, and clinicians will find the intervention usable and feasible to deploy.

To operationalize the main outcome, we will review the EHR for the treatment recommendation made by the PCP and categorize it as: 1) PCP recommendations matches Screening Wizard referral; 2) PCP recommendation partially matches Screening Wizard referral; or 3) PCP recommendation does not match Screening Wizard referral.

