## **Statistical Considerations**

A stepped wedge design was selected for both ethical considerations and feasibility. A stepped wedge cluster randomized trial design involves the sequential random rollout of an intervention over multiple time periods following a “baseline” period when no cluster has been exposed. The crossover is typically in one direction, from control to intervention, and continues until all of the clusters receive the intervention with observations taken from every cluster and at each time period. All 3 studies in the ETUDES Center, and specifically, Screening Wizard, will utilize this design. Prior to study start, each CCP study practice will be randomly assigned to switch from Treatment As Usual (TAU) to the intervention.

In the proposed stepped wedge design, all practices start with TAU (i.e., PCP referral to embedded MH care) and are randomized to transition to implement Screening Wizard at different times. All clinics will be initially monitored for at least 2 months during TAU, followed by a staggered adoption of Screening Wizard. During each time period, a new clinic will begin to use Screening Wizard (order determined by block randomization). A web-based system will randomly assign the next clinic to begin.

Hypothesis 1b: Screening Wizard will increase the rate of personalized referrals, compared to TAU. We will perform multilevel modeling to explore time effects and intervention-level factors associated with Screening Wizard. We will first conduct t-tests for continuous variables and chi-square tests for categorical variables to examine for baseline differences in demographic and clinical variables. We will use generalized linear mixed models (nesting for site) to examine for between-intervention differences in personalized referral rate. Baseline characteristics distinguishing groups will be included as covariates in models examining treatment effects. Criterion for success: 75% of PCP recommendations partially or completely match Screening Wizard personalized referral and there is a 50% increase in number of parents and adolescents who feel their needs were met after the PCP visit during the Screening Wizard phase compared to TAU.

Due to the pilot nature of this study, sample size and power considerations center around the precision of confidence interval (CI) width estimation for feasibility outcomes. In the Development Phase (Aim 1), a sample size of 50 affords us a 95% CI width of no more than 0.28.

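### The needs-met half of the success criterion compares raw counts between phases with no denominator, so passing it depends on enrolment per phase as well as on satisfaction

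*Combined protocol and SAP*

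**What the plan says.** The criterion for success appears twice in the combined protocol and SAP, in the same words, under Hypothesis 1b in Study Objectives and again in Statistical Considerations. It has two conditions joined by *and*. The first is a percentage with a clear denominator: "75% of PCP recommendations partially or completely match Screening Wizard personalized referral". The second is a change in a count, with SW set against TAU: "there is a 50% increase in number of parents and adolescents who feel their needs were met". No denominator is given for the second condition.

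The size of each phase is left open. Study Objectives gives only the total: "We will pilot Screening Wizard in two community pediatric practices using a stepped wedge design (n=2 clinics, 50 adolescents"). Study Design & Methods repeats it: "we will test the feasibility of using Screening Wizard in two community pediatric practices (n=50) using a stepped wedge design". On timing, Statistical Considerations says "All clinics will be initially monitored for at least 2 months during TAU, followed by a staggered adoption of Screening Wizard", and then "During each time period, a new clinic will begin to use Screening Wizard (order determined by block randomization"). That is a minimum length for TAU. The documents give no length for the SW phase, no enrolment quota per phase and no expected number of respondents per phase. The generalized linear mixed model is named for the personalized referral rate only, so it does not supply a denominator for needs-met either.

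**The concern.** A count of satisfied respondents is the product of how many people were asked and how many of them were satisfied. Comparing counts between phases isolates satisfaction only if the same number of people respond in each phase, and nothing in the plan secures that. If SW enrols more youths than TAU, the target can be met with no improvement. If SW enrols fewer, a real improvement of the stated size will probably miss it.

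The documents attach no stop/go consequence to the criterion, so what is at stake is a pilot benchmark that could mislead whoever uses it to judge the tool. The match condition is not in question here.

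**Working it through.** **The plan's own figure.** The only precision figure is a 95% CI width of no more than 0.28 with n = 50. For a proportion of 0.5, the Wald width is 2 × 1.96 × √(0.25/50) = 0.277, so the figure reproduces. It does not bear on the needs-met comparison, for which the plan gives no expected rate, power or precision.

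**What the rule requires.** Let n_TAU and n_SW be the respondents per phase and p_TAU and p_SW the needs-met rates. In expectation the count rule is n_SW·p_SW ≥ 1.5·n_TAU·p_TAU, that is

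p_SW/p_TAU ≥ 1.5 × n_TAU/n_SW.

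This is algebra and needs no assumed rate. For example, 1.5 × 28/22 = 1.91, and 1.5 × 20/30 = 1.00.

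**Chance of passing.** Inputs from the documents: a total of 50 and the 50% increase. Assumed, because the documents do not give them: the split between phases, a TAU needs-met rate of 50%, and one respondent per youth. Clustering and time trend are ignored. X ~ Bin(n_TAU, p_TAU) and Y ~ Bin(n_SW, p_SW) are independent and enumerated exactly. The count rule is Y ≥ 1.5X. The proportion rule is Y/n_SW ≥ 1.5·X/n_TAU. X = Y = 0 counts as a fail.

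| TAU/SW | Rate ratio needed (counts) | No change: counts | No change: proportions | 50% to 75%: counts | 50% to 75%: proportions |
|---|---|---|---|---|---|
| 30/20 | 2.25 | 0.004 | 0.10 | 0.05 | 0.56 |
| 28/22 | 1.91 | 0.02 | 0.08 | 0.17 | 0.50 |
| 25/25 | 1.50 | 0.09 | 0.09 | 0.52 | 0.52 |
| 22/28 | 1.18 | 0.31 | 0.08 | 0.87 | 0.52 |
| 20/30 | 1.00 | 0.52 | 0.10 | 0.97 | 0.51 |

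The two rules agree at 25/25 and nowhere else in the table. These are chances for the needs-met condition alone. Because both conditions must hold, the no-change values are upper bounds for the whole criterion.

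**How likely is an uneven split?** A natural layout for two clinics, assumed here, is three equal periods: clinic A has one TAU and two SW periods, clinic B two TAU and one SW. With Poisson accrual to a total of 50, n_SW ~ Bin(50, q), where q = (2r_A + r_B)/(3(r_A + r_B)) and r_A, r_B are the clinic volumes.

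- *Equal volumes:* q = 0.5, and P(n_SW ≤ 22 or ≥ 28) = 0.48. Averaged over splits, the no-change pass chance is 0.17 on counts and 0.09 on proportions.
- *Volumes 2:1, larger clinic crossing first:* q = 5/9 = 0.556, expected n_SW = 27.8. No-change pass chance 0.35 on counts, 0.09 on proportions.
- *Volumes 2:1, larger clinic crossing second:* q = 4/9 = 0.444, expected n_SW = 22.2. No-change pass chance 0.07 on counts, 0.09 on proportions.
- *Volumes from 1.5:1 to 3:1:* counts 0.27 to 0.45 (larger first) and 0.10 to 0.04 (larger second); proportions 0.09 to 0.10.

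**Sensitivity to the assumed rate.** No change, with a common rate moving from 30% to 80%:

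| TAU/SW | Counts | Proportions |
|---|---|---|
| 28/22 | 0.09 to below 0.001 | 0.17 to 0.003 |
| 25/25 | 0.20 to 0.005 | 0.20 to 0.005 |
| 22/28 | 0.38 to 0.14 | 0.19 to 0.006 |

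**The case against.** The strongest reply is that *number* is loose wording for a proportion. Study Objectives states the needs-met goal as raising a likelihood, Hypothesis 1b concerns a rate, and the other half of the criterion is a percentage. This is probably right about intent. It does not change the criterion, which is written as a count in both places and is not redefined anywhere.

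A second reply is that the size of the effect rests on inputs the documents do not contain: the split, the baseline rate, equal periods, accrual pattern and clinic volumes. Parents and adolescents are also up to two correlated respondents per family, which the calculation does not model. The individual probabilities are therefore illustrative. The dependence on n_TAU/n_SW is not.

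Third, averages soften the picture. With equal volumes and a true rise from 50% to 75%, the pass chance averaged over chance splits is 0.52 on counts and 0.51 on proportions. With 2:1 volumes, averaging over the randomised crossover order gives a no-change pass chance of (0.35 + 0.07)/2 = 0.21 on counts. Both figures are correct. But the trial will be run once, with one split, and at the target effect the chance on counts ranges from 0.05 to 0.97 across the splits tabulated.

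Finally, this is a pilot, the planned model for referral rate is unaffected, and an analyst could report proportions anyway. That limits the consequence. It still leaves a choice between two rules that can disagree to be made after the data are seen.

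**Conclusion.** The concern holds: the needs-met condition is wrong as written. It mixes satisfaction with enrolment, and the plan does nothing to equalise the phases. At 20 TAU/30 SW, unchanged satisfaction meets the target in expectation. At 28/22 a 1.91-fold rise is needed instead of the 1.5-fold rise the plan appears to intend. With an assumed 50% rate, one respondent per youth and no clustering or time trend, a modest imbalance of 22/28 raises the no-change pass chance from 0.08 on proportions to 0.31 on counts. The reverse imbalance, 28/22, cuts the chance of passing at the stated target from 0.50 to 0.17.

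The point should be fixed, though its reach is limited. It affects a pilot benchmark, not participant safety or the model-based comparison of referral rates, and it disappears if the phases turn out exactly equal.

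**What to change.** In Hypothesis 1b, both in Study Objectives and in Statistical Considerations, replace the count with the proportion of responding parents and adolescents in each phase. Keep the sponsor's 50%, and write the word *relative* into the sentence so that it cannot be read as 50 percentage points. For example: *a relative increase of at least 50%, from TAU to Screening Wizard, in the proportion of responding parents and adolescents who report that the visit met their needs*. Record the number of respondents per phase. Report the SW minus TAU difference in proportions with its 95% CI as a pilot estimate; at 25/25 and 50% the half-width is about 1.96 × √(0.25/25 + 0.25/25) = 0.28, ignoring clustering.

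The cost is one sentence reworded in two places, with no new instrument, visit or participant. There are two consequences to accept. The target becomes harder to meet than under the present wording if SW is the larger phase: at 22/28 a true rise from 50% to 75% passes with chance 0.52 instead of 0.87. Also, a 50% relative rise cannot be reached if the TAU proportion exceeds 2/3, since 1.5 × 2/3 = 1. Whether to use another kind of target, or separate criteria for parents and adolescents, is a design choice for the sponsor and not part of this correction.
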